11.5.2.2 Modified SARI severity level and respiratory support severity level

Severity will be assessed in two ways, first by intensive care unit (ICU) admission and in-hospital death outcomes, and through outcomes related to respiratory support.

ICU and in-hospital mortality:

The following three mutually exclusive categories will characterise the worst level of severity of hospitalisation due to SARI:

- 1. Hospital admission without ICU admission and without in-hospital death;
- 2. ICU admission without in-hospital death;
- 3. In-hospital death
 - a. during ICU stay
 - b. outside of ICU stay

As an additional indicator of severity at hospitalisation and throughout hospitalisation, progression risk is defined as proportion of in-hospital deaths and proportion of ICU admissions among all hospitalised SARI patients.

The following categories will complement the characterisation of the severity of hospitalisation due to SARI. For each patient, the highest level of respiratory support ever received during the hospital stay will be reported.

- 1. No respiratory support;
- 2. Oxygen therapy (e.g., nasal cannula, mask);
- 3. Non-invasive ventilation (ventilatory support without tracheal intubation; e.g., high-flow nasal oxygen, Continuous Positive Airway Pressure (CPAP) or Bi-level Intermittent Positive Airway Pressure (BiPAP));
- 4. Invasive mechanical ventilation (ventilatory support with tracheal intubation);
- 5. Extracorporeal membrane oxygenation (ECMO).

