10.2.2 Secondary objectives

- Objective 2: as objective 1, but stratified by:
 - RSV subtype A and B infection (objective 2.1)
 population of special interest (e.g., age groups, gender)⁸ (objective 2.2)
 time since vaccination (objective 2.3)
 calendar time (objective 2.4)
 - modified severity level⁹
 (objective 2.5)

⁹ Severity levels are defined by hospital outcome (intensive care unit [ICU] admission; in-hospital death) and/or respiratory support. As an additional indicator of severity at hospitalisation and throughout hospitalisation, progression risk is defined as proportion of in-hospital deaths and proportion of [ICU] admissions among all hospitalised SARI patients.

⁸ For example, specific age groups, specific immunocompromised or chronic conditions

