11.5.2 Secondary outcomes

The secondary outcomes in patients hospitalised with modified SARI symptoms include:

- detection of RSV subtypes A and B
- modified SARI severity level of study participants (both cases and controls), including respiratory support severity level

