11.9 Covariates

The complete dataset can be found in the id.DRIVE common dataset case report form (eCRF) and is summarised in Table 1. All covariates are being collected for both prospective and retrospective subjects, if available.

Covariate ¹⁷	Description
Age at hospital admission	Years, calculated based on date of birth and date of admission
Gender assigned at birth	Male, female
Chronic conditions*	
Asthma	Binary
	If yes, subcategory 'Mild intermittent', 'Mild persistent',
	'Moderate persistent', 'Severe persistent', 'No information'
Lung disease	Binary
	If yes, subcategory 'COPD' and stage (GOLD I – IV, No
	information)
Cardiovascular disease	Binary
	If yes, subcategory 'Congestive heart failure'
Hypertension	Binary
Chronic liver disease	Binary
	If yes, subcategory 'End-stage liver disease (ESLD)': 'No', 'Yes',
	'No information'
Chronic renal disease	Binary
	If yes, subcategory 'End-stage kidney disease (ESKD)': 'No', 'Yes
	but without dialysis', 'Yes and on dialysis', 'No information'
Diabetes type I	Binary
Diabetes type II	Binary
Obesity	Binary
Cancer	Binary
	If yes, specification of subcategories: 'Solid tumour',
	'Haematological cancer', 'No information'.
	If solid tumour or haematological cancer is yes, further
	specification of cancer type to be selected from list.

Table 1. Study covariates and health care use

¹⁷ Some covariates might not be collected across all Study Contributors. This will be specified in the Study Requestor-specific protocol and SAP after completion of feasibility assessments.

Covariate ¹⁷	Description
Immunodeficiency (or	Binary
organ transplant)	If yes, specification of subcategories: 'Solid organ or islets
	transplant', 'Hematopoietic stem cell transplantation', 'Primary
	immunodeficiency', 'Advanced or untreated human
	immunodeficiency virus (HIV) infection', 'latrogenic
	immunodeficiency', 'Other'. If solid organ or islets transplant is
	yes, specification of subcategories: 'Kidney', 'Liver', 'Intestines',
	'Heart', 'Lung', 'Pancreas', 'Other', 'No information'
Neurological disorders	Binary
Receiving chronic oxygen	Binary (defined as oxygen used for at least 15 h per day in
supplemental therapy	chronically hypoxaemic patients)
Body mass index (BMI)	Continuous
Smoking history	Never smoker, ex-smoker, occasional smoker, daily smoker, no
0 1	information
Vaccination history RSV	Binary
	If yes, was it investigational RSV vaccine, brand, date, and source
	of information
Vaccination history COVID-19	Binary

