	If yes, brand, date, and source of information
Vaccination history influenza	Binary, within 12 months prior to the modified SARI hospital
	admission
	If yes, brand, date, and source of information
Vaccination history	Binary, at least one vaccination in the past
pneumococcus	If yes, brand, date, and source of information
Long-term care facility	Binary, if no, specification of residential situation before
residence	hospitalisation: 'Home', 'Home with nursing care', 'Transfer from
residence	another hospital', 'Rehabilitation centre', 'Nursing home',
	'Other', 'No information'
History of RSV in the current	Binary
season before symptom onset	If yes, date.
leading to this hospitalisation	n yes, date.
Prior modified SARI	Binary,
hospitalisation episode in	If yes, time since most recent prior modified SARI hospitalisation
previous 12 months	n yes, time since most recent phot mounied shar hospitalisation
Month and year of prior SARI	Month and year
episode	
Respiratory support	'None', 'Oxygen therapy', 'Non-invasive ventilation', 'Invasive
	mechanical ventilation', 'Extracorporeal membrane oxygenation
	(ECMO)', 'No information'
ICU admission	Binary, date of admission, date of discharge
In-hospital death	Binary, date of hospital discharge or in-hospital death
Post-discharge destination	'Home', 'Home with nursing care', 'Transfer to another hospital',
	'Rehabilitation centre', 'Nursing home or other long-term care
	facility', 'Other', 'No information'
Length of hospital stay	Days, continuous
Treatments received during	'Antibiotics', 'Antiviral drug(s)', 'Corticosteroid(s)', 'Immune
hospital stay for the	modulator(s)', 'Anti-RSV antibodies', 'Other monoclonal
management of modified	antibodies', 'None of the above'.
-	
SARI episode	Brand name, if anti-RSV antibodies received during hospital stay

Covariate ¹⁷	Description
Treatments received prior to	'Antibiotics', 'Antiviral drug(s)', 'Corticosteroid(s)', 'Anti-RSV
hospital admission for the	antibodies', 'Other monoclonal antibodies', 'None of the above'.
management of current	Brand name, if anti-RSV (or other monoclonal) antibodies
modified SARI episode	received during hospital stay
Medicinal product for the	Binary
prevention of RSV infection	If yes, type ('Antiviral drug', 'Anti-RSV-antibodies', 'Other'),
within 12 months prior to	brand and date (month/year) if anti-RSV-monoclonal antibody
current hospitalisation	
Laboratory results (RSV)	Type of specimen(s), date(s), RSV subtype(s)

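### The respiratory-support severity scale ignores pre-admission support, so severity-specific VE on that axis (objective 2.5) is diluted towards the non-severe value if VE differs by severity

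*Protocol*

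**What the plan says.** Objective 2.5 repeats the primary VE analysis by severity. The footnote in section 10.2.2 states: "Severity levels are defined by hospital outcome (intensive care unit [ICU] admission; in-hospital death) and/or respiratory support".

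Section 11.5.2.2 introduces the respiratory-support scale thus: "The following categories will complement the characterisation of the severity of hospitalisation due to SARI". It then gives the scoring rule: "For each patient, the highest level of respiratory support ever received during the hospital stay will be reported". Level 2 is "Oxygen therapy (e.g., nasal cannula, mask"). Level 3, non-invasive ventilation, includes "Continuous Positive Airway Pressure (CPAP) or Bi-level Intermittent Positive Airway Pressure (BiPAP"). Levels 4 and 5 are invasive ventilation and ECMO. No level requires the support to be new or increased.

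Section 11.5.2 applies the scale to everyone enrolled: "modified SARI severity level of study participants (both cases and controls), including respiratory support severity level".

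Table 1 (section 11.9) collects long-term oxygen as a covariate, "Binary (defined as oxygen used for at least 15 h per day in" patients with chronic hypoxaemia, but nothing links that item to the severity level. Table 1 shows no item for home CPAP or BiPAP. Section 11.9 describes Table 1 as a summary of the eCRF.

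**The concern.** The scale is meant to describe how severe this SARI admission was, but it counts any support used during the stay. A patient on long-term oxygen who carries on with it unchanged is recorded as level 2. A patient who brings a home CPAP or BiPAP device is recorded as level 3. Such patients can be expected: enrolment starts at age 60, and the optional screening codes in section 11.6.2 include chronic lower respiratory diseases.

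The higher strata then mix two kinds of patient, those who deteriorated and those who did not. If the vaccine protects better against severe disease, the mixture gives a VE below the true severe-disease value. Whether VE varies with severity is what objective 2.5 sets out to examine.

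**Working it through.** The protocol states no figure on this point, so there is nothing to reproduce. The calculation below is an illustration. **All its inputs are assumptions**, including the cuts at level 2 or above and level 3 or above, which the protocol does not fix.

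**Inputs.** True VE is 80% where new support is needed and 50% otherwise. New support is needed by 50% of patients (level ≥2) or 15% (level ≥3). Home oxygen is used by 5, 10 or 15% and home CPAP/BiPAP by 3 or 5%. Vaccine coverage is 40% in home-support users and 20% in others. Home-support users escalate as often as others unless stated.

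**Formula.** Take cases as equal to controls among the unvaccinated, and as controls × (1 − VE) among the vaccinated. With same-level controls the unvaccinated terms cancel, so

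apparent VE = 80 − (80 − 50) × w,

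where w is the share of vaccinated controls in the labelled stratum who are home-support users without escalation.

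**Example, 10% home oxygen, per 1,000 controls.** Vaccinated home-oxygen users: 100 × 0.40 = 40, of whom 20 escalate and 20 do not. Vaccinated others who escalate: 900 × 0.20 × 0.50 = 90. So w = 20/130 = 15.4%, and VE = 80 − 30 × 0.154 = 75.4%.

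| Stratum | Home support | w | Apparent VE |
|---|---|---|---|
| ≥2 | 5% | 10/115 = 8.7% | 77.4% |
| ≥2 | 10% | 20/130 = 15.4% | 75.4% |
| ≥2 | 15% | 30/145 = 20.7% | 73.8% |
| ≥2, 80% of home-oxygen users escalate | 5% | 4/115 = 3.5% | 79.0% |
| ≥2, 80% of home-oxygen users escalate | 15% | 12/145 = 8.3% | 77.5% |
| ≥3 | 3% | 10.2/41.1 = 24.8% | 72.6% |
| ≥3 | 5% | 17/48.5 = 35.1% | 69.5% |
| ≥3, coverage 20% in everyone | 3% | 5.1/35.1 = 14.5% | 75.6% |
| ≥3, coverage 20% in everyone | 5% | 8.5/38.5 = 22.1% | 73.4% |

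The loss is therefore 1.0 to 6.2 points for level ≥2 and 4.4 to 10.5 points for level ≥3. The level ≥3 range holds escalation among home CPAP/BiPAP users at 15%. If 80% of them escalated, with 5% home use, w would be 4/48.5 = 8.2% and VE 77.5%.

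**Adjustment.** Mantel-Haenszel stratification on home support, with same-level controls, gives 77.9, 76.1 and 74.6% for level ≥2 at 5, 10 and 15%, and 74 to 71% for level ≥3 at 3 to 5%. Adjustment removes little, because the stratum itself is mixed.

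**All controls as comparator, unadjusted.** Level ≥2 at 10%: 1 − (32/420)/(220/780) = 73.0%. Level ≥3 at 5%: 1 − (14.8/144)/(210/790) = 61.3%; at 3% it is 67.7%. Adjustment for home support brings the level ≥3 figures back to 74 to 76%.

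**When there is no effect.** With VE at 80% in both severities, the formula gives 80 − 0 × w = 80% for any w. With all controls it is also 80% once home support is adjusted for, or if home support is unrelated to vaccination.

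**Milder gradients.** Take 15% escalating, 2 to 10% on chronic support, and coverage of 30% throughout or 50% in supported patients. Then w runs from 5.1/50.1 = 10.2% to 42.5/90.5 = 47.0%. True values of 80% against 70% give 79.0 to 75.3%, and 80% against 60% give 78.0 to 70.6%.

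**The case against.** The case on the other side has several parts, and most of it limits the point rather than removing it.

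- **Same rule for cases and controls.** True, and it makes a same-level comparison possible. It does not unmix the stratum, so dilution remains wherever VE differs by severity.
- **Every input is assumed.** This stands. The escalation rate in home-support users matters most: at 80% escalation the level ≥2 loss falls to 1.0 to 2.5 points.
- **Chronic oxygen is already collected, and the SAP can add analyses.** This stands for home oxygen. It does not hold for home CPAP/BiPAP if the eCRF, like Table 1, has no such item.
- **The scope is narrow.** This stands: it concerns one of two severity axes in one of five secondary sub-objectives.

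A reader might infer that a severity gradient would be hidden. The illustration does not show that. With same-level controls the lower stratum stays at 50%, so a true 30-point difference shrinks to roughly 20 to 29 points. A reader might also take 61 to 68% for level ≥3 as the size of the problem. Those are unadjusted values against all controls, and much of that gap is confounding, whereas section 11.12.4 commits to adjusting for comorbidities. Finally, section 13 might be read as saying that chronic lung patients are vaccinated first. It refers only to specific chronic conditions and does not name lung disease or home-support users. The dilution does not need that link, as the equal-coverage rows show.

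**Conclusion.** The rule in section 11.5.2.2 places patients with unchanged home support in higher severity levels. This is a consequence of the stated definition, not of missing detail. If VE differs by severity, respiratory-support-specific VE in objective 2.5 is attenuated towards the non-severe value: about 1 to 6 points for level ≥2 and 4 to 11 points for level ≥3 with same-level controls, under an assumed 80% against 50%.

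It would go too far to say that the estimate is biased in any event. The protocol gives no prevalence of home support, and there is no bias if VE is equal across severities and chronic support is either adjusted for or unrelated to vaccination. The ICU/in-hospital-death axis and the primary objective do not use this rule and stand as they are.

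**What to change.** For the respiratory-support axis of objective 2.5:

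1. Pre-specify a sensitivity analysis that excludes patients with the Table 1 chronic-oxygen item from the level 1 versus level 2 split. The data are already collected.
2. Add one eCRF item for pre-admission CPAP/BiPAP, if the full eCRF lacks it, so that continued home ventilation is not counted as level 3.
3. Do not rescore chronic-oxygen patients to level 1 on the present fields. The chronic-oxygen item is binary and in-hospital oxygen is a single category, so a patient whose oxygen need rose looks the same as one with no change. Rescoring would misclassify true escalation in the other direction. It becomes possible only if the eCRF also records whether oxygen was increased over baseline (yes/no).

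The cost is a slightly smaller sample in the sensitivity analysis and one or two extra items from the same medical record. These are changes to outcome measurement and do not touch patient care.

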11.6 Definitions

11.6.1 'Hospitalised patient'

A 'hospitalised patient' is defined as a person admitted to the hospital with overnight stay¹⁴. In case of referral to another hospital, the date of hospital admission is defined as the date of first admission.

¹⁴ The patient is hospitalised for minimum one whole night ("one overnight stay").

11.6.2 'Modified SARI patient'

A 'modified SARI patient' is defined as a person hospitalised with a suspicion of a respiratory infection with at least one of the following symptoms:

- cough
- shortness of breath
- fever (≥38 C^o)

with symptom onset within the last 10 days prior to the current hospital admission. This SARI definition is modified from the latest ECDC case definition [15]. Sensitivity analysis will be done applying the WHO-RSV case definition¹⁵ and id. DRIVE case definition¹⁶.

Additionally, the International Classification of Diseases (ICD)-10 codes and corresponding definitions listed below could be used as a guideline to identify potential modified SARI patients (i.e., for screening), if deemed appropriate at specific Study Contributors:

- J00-J06: Acute upper respiratory infections
- J21.0, J21.8, J21.9: Bronchiolitis
- J12-J18: Pneumonia
- J20-J22: Other acute lower respiratory infections
- J40-J47: Chronic lower respiratory diseases

11.6.3 'Study participant'

A 'study participant' is defined as a patient who meets the 'hospitalised patient' AND 'modified SARI patient' definitions, AND fulfils all the inclusion criteria but none of the exclusion criteria.

11.6.4 'Case' ('test-positive case')

'Cases' are study participants who meet the 'modified SARI patient' definition AND have tested positive for at least one RSV RT-PCR or similar molecular assays, with specimens collected within 10 days prior and up to 72 hours after hospital admission. Test-positive cases include laboratory-confirmed coinfections.

¹⁶ An id.DRIVE definition of SARI (defined as requiring hospitalisation with a suspicion of a respiratory infection with symptom onset within the last 14 days prior to hospital admission, having at least one of the following symptoms: cough, shortness of breath, fever (\geq 38 C°) or sudden onset of anosmia, ageusia or dysgeusia) will be used in sensitivity analyses. This SARI definition is modified from the latest ECDC case definition (specifying "suspicion of respiratory infection"). [EUROPEAN CENTRE FOR DISEASE PREVENTION AND CONTROL (2023). Core protocol for ECDC studies of COVID-19 vaccine effectiveness against hospitalisation with Severe Acute Respiratory Infection, laboratory-confirmed with SARS-CoV-2 or with seasonal influenza - Version 2.0. Available from: https://www.ecdc.europa.eu/en/publications-data/core-protocol-ecdcstudies-covid-19-vaccine-effectiveness-against-0 [Accessed: 17-08-2023]].

¹⁵ A World Health Organisation (WHO)-expanded definition of RSV-SARI (severe disease – defined as requiring hospitalisation AND acute – defined as onset within the last 10 days AND respiratory infection – defined as having at least one of the following: shortness of breath or cough) will be used in sensitivity analyses. [Source: https://www.who.int/teams/global-influenza-programme/global-respiratory-syncytial-virus-surveillance/case-definitions]

11.6.5 'Control' ('test-negative control')

'Controls' are study participants who meet the 'modified SARI patient' definition AND have all respiratory samples being negative for RSV RT-PCR or similar molecular assays, with specimen(s) collected between 10 days prior to and up to 72 hours after hospital admission. Test-negative controls include study participants negative for other pathogens and study participants positive to other pathogens based on specimen(s) collected between 10 days prior to and up to 72 hours after hospital admission.

11.7 Identification of modified SARI patients

Modified SARI patients will be identified based on the 'modified SARI definition' (section 13.6.2) either prospectively (e.g., during consultation in the emergency department (ED) or at admission to an infectious disease or internal medicine hospital ward) or retrospectively by hospital database search or from respiratory samples sent to the virology laboratory.

11.8 Exposure

11.8.1 Exposure definitions

11.8.1.1 'Vaccinated with [RSV vaccine name] during the study period of interest'

'Vaccinated' study participants were vaccinated with exposure of interest: e.g. single dose/primary vaccination/at least one dose of RSV vaccine of interest during the epidemiological year(s) of interest, within the appropriate timeframe for the product to be **effective** prior to modified SARI symptom onset.

11.8.1.2 'Unvaccinated with [RSV vaccine name] during the study period of interest'

'Unvaccinated' study participants did not receive any exposure of interest: e.g. single dose/primary vaccination/at least one dose of RSV vaccine of interest during the epidemiological year(s) of interest.

11.8.1.3 'Recently vaccinated with [RSV vaccine name] during the current RSV season'

'Recently vaccinated' study participants were vaccinated with exposure of interest: e.g. single dose/primary vaccination/at least one dose of RSV vaccine of interest during the epidemiological year(s) of interest, within the appropriate timeframe for the product to be **ineffective** prior to modified SARI symptom onset.

11.8.1.4 'Other'

Additional vaccine exposure definitions might be defined depending on the real-life use of the RSV vaccines.

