- Vaccinated with RSV vaccine during the study period of interest': vaccinated with exposure of interest: e.g. single dose/primary vaccination/at least one dose of the RSV vaccine during the epidemiological year(s) of interest, within the appropriate timeframe for the product to be **effective** prior to modified SARI symptom onset.
- Unvaccinated with RSV vaccine during the study period of interest': did not receive any RSV vaccine during the epidemiological year(s) of interest.
- 'Recently vaccinated with RSV vaccine during the current RSV season': Vaccinated with *exposure of interest: e.g. single dose/primary vaccination/at least one dose* of the RSV vaccine during the epidemiological year(s) of interest, within the appropriate timeframe for the product to be **ineffective** prior to modified SARI symptom onset.
- 'Other':

additional vaccine exposure definitions might be defined depending on the real-life use of the RSV vaccines.

Data sources, data collection

The study uses a combination of primary (e.g., specific laboratory results, vaccine cards) and secondary data sources (e.g., existing hospital databases, vaccine registries and linked data).

After study enrolment, data will be collected directly from the patient or by consulting medical records. Information to be collected at minimum includes date of modified SARI symptom onset, date of hospitalisation, respiratory specimen testing results, and information on the potential confounders and effect modifiers.

Exposure status, RSV vaccine information and date(s) of vaccination(s) will be ascertained by consulting vaccination registries, vaccination cards or medical records (depending on the country and region). Where needed, treating physician or other health care professionals will be contacted to obtain additional information.

Context information on national/regional vaccination recommendations and RSV vaccine label information will be collected from external sources.

Covariates

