9 RATIONALE AND BACKGROUND

Respiratory syncytial virus (RSV) is a common pathogen causing respiratory tract infections [3], and its burden is increasingly recognised among older adults. In high-income countries, RSV-related annual hospitalisations were estimated to be 787,000 in 2021 [4], with an annual hospitalisation rate of 145 per 100,000 for RSV-associated acute respiratory infections in adults \geq 60 years of age [5]. In older adults, RSV case fatality proportion was estimated to be 8% [6], with both hospitalisation and mortality rates found to be comparable to influenza [7]. Adults with underlying medical conditions [8, 9] and frailty [10, 11] are at higher risk for hospitalisation and death, potentially due to exacerbation of existing chronic conditions, such as chronic obstructive pulmonary disease and congestive heart failure.

RSV has two main subtypes: A and B, with either of them predominating in a given season, although they may circulate simultaneously in the population [12]. In temperate climates, RSV typically follows a distinct seasonal pattern, with a peak between December and February. Reverse transcriptasepolymerase chain reaction (RT-PCR) and (PCR-based) point-of-care (POC) tests are the gold-standard for the diagnosis of RSV infections. Rapid antigen detection tests (RADT) are also used for the RSV diagnosis, as they require less time and resources, but have a lower sensitivity [13]. Clinical severity is strongly associated with viral load, which declines seven days after inoculation [14].

The development of safe and efficacious vaccination products is essential in addressing the public health impact of RSV-associated illness. Two protein-based vaccines have been approved for use in adults 60 years and older. As of 20 November 2023, the following RSV vaccines are authorised for use in the EU: Arexvy[®] (GSK) and Abrysvo[®] (Pfizer).

Although the efficacy of RSV vaccines has been investigated thoroughly during clinical trials, continuous evaluation of product-specific vaccine effectiveness (VE) under real-world conditions once used as part of the national immunisation programmes (NIPs) remains crucial. Real-world studies allow for the evaluation of more rare outcomes such as hospitalisation. Additionally, duration of vaccine-induced protection, differential VE based on RSV subtypes, and VE in risk groups such as immunocompromised or patients with chronic conditions can be assessed.

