10.2 Research objectives

10.2.1 Primary objective

Objective 1: to estimate brand-specific RSV VE against hospitalisation due to laboratoryconfirmed RSV infection in severe acute respiratory infection (modified SARI) older adult patients.

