11.8.2 Exposure ascertainment

Information on all prior RSV vaccine doses will be collected. Vaccination status, vaccination date, vaccine dose and vaccine name and brand information are required. Depending on the Study Contributor, the source for exposure ascertainment will be different and may include vaccination registries, medical records, or vaccination cards. Information on the source documentation of the exposure ascertainment will be collected.

Patients that cannot be classified into one of the exposure categories (i.e., their vaccination status is unknown) will be excluded.

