for 'cases to controls' ratio r, coverage γ , total number of subjects N, and where z_{α} and z_{β} are the standard normal z-scores for the type I and type II error rates²⁰.

For case-control studies with multiple exposure categories (k > 2), 3 generic exposure categories exist: (1) the exposure group of interest, (2) the appropriate comparator group and (3) other exposure groups not relevant for the comparison, resulting in a $3x^2$ cross table. Starting from the assumptions on the case-control ratio and on the proportions of subjects belonging to each of the three exposure categories (derived from assumptions on brand-specific vaccination coverage, overall vaccination coverage and vaccination history), the relative cell frequencies of the $2x^2$ table of interest can be derived, based on which all parameters required for sample size calculations are derived.

Simulation-based approach

Data generation workflow

Notation

Before describing the data generation workflow, the following parameters which act as input for the model have to be defined:

- 1. $VE_{x,overall}$: the overall VE of exposure x, the corresponding odds ratio is $OR_{x,overall} = 1 - \frac{VE_{x,overall}}{100}$.
- 2. c = P(unexposed | control): proportion of unexposed subjects among the controls
- 3. $P_x = P(exposure \ x | exposed, control)$: brand share of exposure x among the exposed
- 4. *r*: ratio of cases to control (that is, number of cases per one control)

General set-up

In each simulation run, a dataset is constructed by combining data generated for a number of individual Study Contributors. We will denote the total number of Study Contributors as k and the total sample size as N. Additionally, it is assumed that each Study Contributor contributes the same number of subjects, i.e. $\frac{N}{k}$. In order to allow for variability in the underlying vaccine effects across Study Contributors, the VE can be different from Study Contributor to Study Contributor. In the next section, it is described how data for one Study Contributor is generated given the Study Contributor-specific VEs for all exposures. The subsequent section describes how the VE are varied across the Study Contributors to introduce between-Study Contributor variability.

Simulating data at the Study Contributor level

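### Section 11.8.1.2 defines 'unvaccinated' against the brand of interest only, contradicting the abstract and Annex 1; applied as written, it biases brand-specific VE downwards where another brand is in use and protective

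*Protocol*

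**What the plan says.** The primary objective in section 10.2.1 is "to estimate brand-specific RSV VE against hospitalisation due to laboratoryconfirmed RSV infection". The reference group for that estimate is described in three places.

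- **Section 11.8.1.2 (body):** unvaccinated "study participants did not receive any exposure of interest: e.g. single dose/primary vaccination/at least one dose of RSV vaccine of interest", within the epidemiological year(s) of interest. It is silent on other RSV brands.
- **Abstract, Exposure:** unvaccinated participants "did not receive any RSV vaccine during the epidemiological year(s) of interest".
- **Annex 1, analytical approach:** with more than two exposure categories, the participants divide into the exposure of interest, the comparator, and "3) other exposure groups not relevant for the comparison". Only the first two form the 2x2 table.

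Two further provisions in the body could affect where an other-brand recipient is placed. On the 'Other' category, section 11.8.1.4 says: "Additional vaccine exposure definitions might be defined depending on the real-life use of the RSV vaccines". On exclusion, section 11.8.2 says: "Patients that cannot be classified into one of the exposure categories (i.e., their vaccination status is unknown) will be excluded".

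Section 9 notes that "Two protein-based vaccines have been approved for use in adults 60 years and older", and section 13 expects the vaccine market to fragment further.

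**The concern.** A recipient of another RSV brand has a known vaccination status and has not received the vaccine of interest. Under 11.8.1.2 that person is unvaccinated, whereas under the abstract and Annex 1 that person is not in the reference group. The same patient is therefore classified in two ways for the primary analysis.

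Nothing else in the body settles the matter. The 'Other' category is optional and does not mention other brands, and the exclusion in 11.8.2 reaches only patients whose status is unknown.

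At stake is what the reported VE means. If other-brand recipients sit in the reference group, the contrast is no longer vaccine versus no RSV vaccine. It becomes vaccine versus a mixture of unvaccinated people and people protected by another product. The result then depends on how widely the other brand is used, and it is a different quantity from the one on which the Annex 1 sample size is built.

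**Working it through.** The protocol states no figure that bears on this point, so there is none to reproduce. The check uses the exposure model of Annex 1.

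**Inputs**

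- From the protocol: VE = 1 − OR (section 11.12.4). In Annex 1, controls are unexposed with probability c and exposed to brand x with probability (1 − c)·Pₓ; the exposure odds in cases, relative to unexposed, are those of controls multiplied by the brand's OR.
- Assumed, because section 11.10 leaves them to the Study Team: total coverage, brand shares, and the VE of each brand.

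**Formula**

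Let the control proportions be a (brand of interest), b (other brand) and u = 1 − a − b (no RSV vaccine). Cases are then in the proportions a·ORₓ : b·OR_other : u.

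- Abstract and Annex 1 reference (u only): OR = ORₓ, so the estimate equals the true brand VE.
- Section 11.8.1.2 reference (u + b): OR_body = [a·ORₓ / (u + b·OR_other)] ÷ [a / (u + b)] = ORₓ / (1 − q + q·OR_other), where q = b / (u + b) is the other-brand share among controls labelled unvaccinated.

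If OR_other < 1 and q > 0, the denominator is below 1, so OR_body > ORₓ and VE falls. If q = 0 or OR_other = 1, nothing changes.

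**Both brands with a true VE of 70% (OR 0.30)**

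| Total coverage | Brand of interest / other | q | 1 − 0.70q | OR_body | VE under 11.8.1.2 |
|---|---|---|---|---|---|
| 5% | 2.5% / 2.5% | 0.025/0.975 = 0.026 | 0.982 | 0.305 | 69.5% |
| 20% | 16% / 4% | 0.04/0.84 = 0.048 | 0.967 | 0.310 | 69.0% |
| 20% | 10% / 10% | 0.10/0.90 = 0.111 | 0.922 | 0.325 | 67.5% |
| 40% | 20% / 20% | 0.20/0.80 = 0.250 | 0.825 | 0.364 | 63.6% |
| 50% | 10% / 40% | 0.40/0.90 = 0.444 | 0.689 | 0.435 | 56.5% |

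**Unequal effectiveness**

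- Brand of interest 50%, other brand 80%, equal shares, 40% coverage: 0.50 / (1 − 0.25 × 0.80) = 0.625, so VE is 37.5% instead of 50%.
- Most extreme combination tried (coverage 60%, brand of interest 20% of doses, VE 50% versus 90%): q = 0.48/0.88 = 0.545 and 0.50 / (1 − 0.545 × 0.90) = 0.982, so VE is 1.8% instead of 50%.
- Other brand with VE 0%: VE stays at the true 70%.

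**The case against.** The strongest reply is that the protocol does not adopt the contaminated reference group. The abstract excludes it. Annex 1 sets other exposures apart, models each brand against the unexposed, and restricts each simulated dataset to the data of interest. Section 16.3 counts recipients of any brand separately from recipients of the brand of interest. Section 11.8.1.2 is template text with placeholders, to be completed in Study Requestor-specific protocols. The 'Other' category could hold other-brand recipients, the abstract provides for an expert group to classify exposure, and all prior RSV doses are collected with brand, so the reference group can still be set correctly at analysis.

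Much of this stands. A reader might infer from 11.8.1.2 that the study has chosen to count other-brand recipients as unvaccinated, and that its VE will therefore be biased. The document does not support that: it contradicts itself, and the bias is conditional on the one sentence being applied as written. A reader might also infer that derived protocols will copy 11.8.1.2, and that results from different Study Requestors will therefore not be comparable. Nothing in the protocol says that 11.8.1.2 takes precedence over the abstract.

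What the reply does not do is resolve the conflict. The safeguards are optional or carry no rule for other brands, and the sentence at issue is the formal exposure definition in the methods section.

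**Conclusion.** The contradiction is real and concerns the reference category of the primary exposure. It needs correcting in a Master Protocol whose purpose is to harmonise exposure definitions across derived protocols.

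The direction of the bias is certain under two conditions: 11.8.1.2 is applied literally, and another protective brand is in use. VE is then too low. The size cannot be fixed from the document. With equal true VEs of 70% and equal shares, the loss is about half a point at 5% coverage, 2.5 points at 20% and 6.4 points at 40%. It reaches 13.5 points when the other brand is four times as common (40% versus 10% of controls). It is larger if the other brand is the more effective one, and small where coverage is low or the brand of interest dominates. These figures assume the Annex 1 exposure model, with no confounding and correct brand recording.

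**What to change.** Align 11.8.1.2 with the abstract: unvaccinated means no RSV vaccine of any brand during the epidemiological year(s) of interest. Keep that time window. Without it, someone vaccinated with the brand of interest in an earlier year would be neither vaccinated under 11.8.1.1 nor unvaccinated, and the estimand would change for a reason unrelated to this point.

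In 11.8.1.4, name recipients of another RSV brand as an explicit category and state that they are left out of the brand-specific comparison, as Annex 1 already assumes.

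The cost is a sentence or two in the Master Protocol and in any derived protocol that carries the current wording. The reference group becomes somewhat smaller. No new data are needed, because section 11.8.2 already requires vaccine name and brand.
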